2.0 Background**BACKGROUND AND SIGNIFICANCE**

Deficits Associated with stroke: Stroke is the leading cause of long-term disability in the United States, affecting approximately 795,000 people each year, with a surviving cohort of nearly 6.5 million.¹ Seventy-three percent of those surviving stroke will have some degree of long mobility deficits,² and less than 50% of survivors progress to independent community ambulation.³ Even among those who achieve independent ambulation, significant residual deficits persist in balance and gait speed, with 60% of persons post-stroke reporting limitations in mobility related to walking.^{4,5} Improving walking is the most often stated goal of patients immediately following a stroke⁶ and after discharge to the community,⁷ and interventions designed to maximize functional ambulation skills are critical to promote activity and social reintegration.⁸ The ability to walk an adequate distance at sufficient speed is a critical predictor of mortality, cardiovascular disease, and mobility disability⁹ and improving gait function has the potential to improve the quality of life of the 15,000 Veterans who survive stroke annually.¹⁰

Anterior propulsion is critical for retraining walking: Generation of forces required to propel the body forward during walking is an essential requirement of locomotion.¹¹ We developed the measure, paretic propulsion (Pp) to quantify this crucial force generation in those with post-stroke hemiparesis and it has emerged as perhaps the most used mechanistic measure of walking performance. Pp describes the contribution of the paretic leg in propelling the center of mass (COM) forward during walking and is defined as the percentage of propulsion performed by the paretic leg.¹² The percentage of propulsion generated by the paretic leg is calculated by dividing the total propulsive impulse (the positive time integral of the anterior/posterior force curve) performed by the paretic leg by the sum of the propulsive impulse performed

by both legs (see Preliminary Studies). Importantly, Pp has relatively little dependence, if any, on walking speed. Propulsion is associated with the muscle activity in the plantarflexors, with increased gastrocnemius and soleus electromyographic activity relating to increased propulsion of the paretic limb.¹³ This increased activity in the muscles that contribute to propulsion is also associated with improvements in functional walking tasks, while increased activation in the non-paretic muscles is associated with increased compensatory behavior.¹⁴ In addition, propulsion is improved by increasing the posterior position of the trailing leg relative to the full body center of mass.¹⁵ However, early activation of flexor muscles such as the tibialis anterior and the rectus femoris are inversely related to propulsion, implying that coordination between flexors and extensors is required to optimize the mechanics of propulsion. Kinematically, hip extension increases the anteriorly directed force and is a significant positive predictor of Pp.¹⁶ Since Pp is influenced by many different biomechanical measures, we believe that it represents the coordinated output of the paretic leg. The measure has been used in over 40 examinations of hemiparetic walking and recently therapies have targeted propulsion as a primary outcome¹⁷ and predictor of gait outcomes.¹⁸ This proposal aims to not only expand the use of propulsion to define the motor control deficit but also to indicate an intervention tailored to specifically to that pattern of deficit in order to improve the overall effects of the intervention.

Relevance to the VA: According to the 2014 VA Stroke Quality Enhancement Research Initiative (QUERI), approximately 15,000 VA admissions occur each year for acute ischemic stroke, with a cost approaching \$275 million in the first 6 months.^{10,19} As the stated mission of the Stroke-QUERI is to “improve care and outcomes for Veterans at risk of ischemic stroke and those who have sustained an ischemic stroke,” it is imperative to develop interventions and frameworks to manage care efficiently and optimize outcomes. The VA stroke clinical practice guideline strongly recommends a comprehensive motor recovery program early in stroke rehabilitation “emphasizing progressive difficulties, repetition, and functional task practice.”²⁰ This guideline further suggest that motor recovery interventions, including ambulation interventions, should include cardiovascular fitness and strengthening.²⁰ In addition, the VA Blueprint for Excellence lists as one of its primary strategies to “advance health care that is personalized, proactive, and patient-driven, and engages and inspires Veterans to their highest possible level of health and well-being.”²¹ Interventions that are specifically tailored to baseline biomechanical assessments, that are designed to improve force production and cardiovascular status via task-specific training, and are translatable to VA clinics and beyond meet the critical needs of the VA in support of its Veterans with stroke.

INNOVATION

Biomechanical Definition of Motor Control Deficits: We have biomechanically defined post-stroke walking patterns based on Pp: 1) low Pp is the predominant pattern and is associated with increased and early paretic flexor EMG activity, lengthened paretic step length, and decreased paretic hip extension^{13,22}; and 2) high Pp pattern is characterized by increased paretic extensor EMG during terminal stance, shortened paretic step length, and prolonged paretic hip extension^{13,22} (see Preliminary Studies for how these are defined).²³ This project will focus on the comparison between high and low Pp, as those with symmetric propulsion represents a small portion of the population with post-stroke deficits.

Treatment Determined by Baseline Motor Control Deficit: Our pilot data reveal that the two patterns are most effectively rehabilitated by different treatment strategies: 1) low Pp by walking on an inclined treadmill requiring increased force production and promoting increased and symmetrical hip extension^{24,25}; and 2) high Pp by walking on a declined treadmill, limiting hip extension and promoting effective stance to swing transitions, increasing knee flexion, and encouraging improved knee extensor eccentric control.^{24,25}

Manipulation of Task Mechanics to Meet Specific Training Goals: Successful uphill walking requires increased force production bilaterally in order to maintain forward progression. Specifically,

spatiotemporal symmetry and paretic hip extension are increased following incline walking post-stroke when the incline is at least eight degrees.²⁶ Ground reaction forces and joint moments increase with concomitant increases in slope, particularly in the anterior-posterior direction representative of propulsion,²⁷ and incline walking is associated with increased knee extensor and ankle plantarflexion activity producing the additional propulsion required to step uphill.²⁸ Gama et al. recently trained individuals post-stroke with body-weight support (BWS) and a 10% incline and compared to a group undergoing level treadmill training with BWS.²⁹ Incline-trained individuals demonstrated significant improvements over the control group in walking speed ($p=0.002$) and paretic step length ($p=0.02$). However, all individuals trained at the same direction of treadmill inclination.²⁹

Although less studied, downslope walking has also been utilized in the training of individuals after neurologic injury. Incline and decline training are both associated with improved endurance, overground walking speed, and dynamic balance control.³⁰ Randomized controlled trials in individuals with Parkinson's Disease³¹ and Multiple Sclerosis³² demonstrate significant improvements associated with downhill walking in mobility, functional activities, balance, and strength of the knee extensors. This knee extensor strength improvement primarily is associated with improved eccentric control of the knee extensors, and the trailing limb increases negative (eccentric) work production with increased slope of the treadmill.³³ The increased negative work production at the knee is likely associated with the decline training effects of increased knee flexion and improved stance to swing transitions. Electromyographic and kinetic analyses demonstrate an increase in power absorption during downslope walking and increases in extensor activity, representative of increased eccentric control of the knee extensors.^{27,34} Downslope walking is also effective in the examination of spinal neurophysiology, demonstrating decreases in spinal level excitability in neurologically healthy adults.³⁵ In addition, acceleration of the center of mass (see Preliminary Studies) is significantly increased in the transition from stance to swing,^{24,25} further indicating the viability of this treatment for individuals with deficits related to decreased knee flexion, poor power absorption, and difficulty transitioning from stance to swing.

Predicting Responders to a Novel Locomotor Rehabilitation Intervention: Many types of locomotor rehabilitation techniques (activity-based therapies,³⁶ lower extremity strengthening,³⁷ aerobic conditioning,³⁸ functional electrical stimulation³⁹) produce robust changes in functional outcomes such as increased self-selected walking speed (SSWS). However, no single intervention is shown to be superior in producing these functional changes.⁴⁰ In addition, a critical need exists to be able to understand mechanisms associated with recovered function in order to predict responders from non-responders prior to a therapeutic intervention. Currently, mechanistic outcomes are too inconsistently applied to locomotor rehabilitation interventions to draw clear conclusions as to how recovery is generated.^{41,42} Recent analyses have begun to examine the patterns of response in rehabilitation participants in an effort to delineate which participants respond to an intervention and how they improve.⁴³⁻⁴⁵ These analyses, however, typically lack a thorough outcome battery that includes broad-based biomechanical and clinical outcome measures. We believe that a full battery of biomechanical and clinical variables will prove crucial for determining a broader set of factors contributing to response to rehabilitation interventions that clinicians can apply to improve decision making regarding intervention selection. This proposal is guided by the overall hypothesis that when provided an intervention tailored to the baseline motor control deficit, there will be fewer non-responders leading to more robust functional effects.

3.0 Intervention to be studied

Intervention

Personalized Intervention: Each participant will be randomized to receive either INCLINE, DECLINE, or CONTROL training. During training, each participant will be asked to walk without an assistive device or ankle-foot orthosis (although an AirCast will be allowed for medial-lateral stability if necessary). For all INCLINE and DECLINE training, individuals will walk for 20 minutes at a 10-degree treadmill tilt, stopping each five minutes for monitoring of vital signs (see “Vital Sign Monitoring” below). As many subjects post-stroke take a beta blocker or other medications that prevent heart rate and blood pressure increases during exertion, a rating of perceived exertion (RPE, must be below “very hard”) will also be collected and adverse events will be strictly monitored. For DECLINE training, the treadmill will be tilted to 10 degrees with the belt reversed and the participant facing in the opposite direction. While participants will be allowed to support themselves with the use of handrails for balance as required, they will wear a climbing harness attached to an overhead support system to prevent falls and thus minimize handrail use. Our previous work was completed at 8 degrees of tilt (see Preliminary Studies), based on work by Werner et al. demonstrating that 8 degrees was required to improve gait symmetry and hip extension in patients with stroke.⁴⁶ Subsequent reports^{29,47} demonstrate that 10 degrees is equally feasible and offers a more intense training opportunity. Individuals will walk at a speed at least 50% of their current overground SSWS, determined at the beginning of each training week, but training as fast as they feel comfortable up to the overground SSWS. Pilot work demonstrated that individuals are not capable of walking on the INCLINE or DECLINE at the overground SSWS secondary to the increased workload associated with the treadmill tilt. Each INCLINE and DECLINE session will be followed by one 6-minute bout of overground walking training as fast as comfortable for each participant focusing on specific gait details targeted in the INCLINE/DECLINE trials (e.g. increased hip extension, increase paretic leg loading, or improved stance to swing transition).

Vital Sign Monitoring: For all training groups, criteria for termination of training include subject complaints of shortness of breath, light-headedness, confusion, severe headache, or dyspnea; onset of angina; excessive blood pressure (systolic BP > 200mm Hg, diastolic BP > 110 mm Hg), or drop in systolic BP > 10 mm Hg and inappropriate bradycardia (drop in heart rate > 15 bpm).^{48,49} In addition, we will stop training for a rest break if the RPE exceeds “very hard” (17 on a 6-20 scale).

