10.0 Study Design / Methods

This proposal seeks to develop a theory-based clinical decision-making framework for the training of walking recovery after stroke based on how different biomechanical patterns of walking illustrate distinct motor control deficits. 72 individuals with unresolved propulsion asymmetry after chronic stroke (greater than six months post-stroke, so additional natural recovery is not expected) will be evaluated to determine their baseline level of Pp: low Pp (≤ 0.47) and high Pp (≥ 0.53) (0.47 to 0.53, equal to 3 standard deviations around the mean for healthy controls). Individuals will be randomly assigned to one of three intervention groups (INCLINE, DECLINE, or CONTROL training), and we will recruit into each training group an equal number of 10 individuals with low or high Pp (Figure 6). Each participant in INCLINE training will walk four 5-minute bouts at the highest speed they can tolerate for 5 minutes (up to SSWS and at least 50% of SSWS) on a 10% up-sloped treadmill followed by 6 minutes of level overground walking at the pace that they can maintain (breaks are allowed as necessary while the clock continues to run). INCLINE training will focus on increasing force production and promoting increased and symmetrical hip extension. Those in DECLINE training will also walk with the same number of bouts, intensity, and overground walking as INCLINE on a 10% down-sloped treadmill, limiting hip extension, and promoting effective stance to swing transitions through increased knee flexion and eccentric control of the knee. During the 6-minute walk, each participant will focus on specific gait details targeted in the INCLINE/DECLINE trials (e.g. increased hip extension, increase paretic leg loading, or improved stance to swing transition). CONTROL participants will walk four 5-minute bouts at their SSWS on a flat treadmill followed by 6 minutes of level overground walking at the SSWS, controlling for equal time of walking activity. Placement into the INCLINE, DECLINE, or CONTROL training groups will be randomized based on a computerized randomization by the study statistician. Each individual will complete 12 sessions (three times a week for four weeks). Clinical and biomechanical outcome measures will be collected pre- and post-training and after a one-month follow-up period. In addition, we will collect a battery of clinical outcome measures before and after training. Spatiotemporal variables (including SSWS) will be collected before and after each session. All clinical and biomechanical assessments will be conducted by an evaluator blinded to training group allocation.

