[name] has been granted permission to break the blind of the data to ensure that randomization to each group is not harmful to the participants. This plan is thoroughly described in the Research Plan and Human Subjects sections. All serious adverse events will be analyzed by the investigative team and the MUSC Institutional Review Board. Serious adverse events are defined as 1) being unexpected; 2) related to a subject’s participation in research; and 3) that subjects are at greater risk of harm than was previously recognized. If greater than 10% in each cell have a serious adverse event, we will evaluate the circumstances and decide if the event was caused by a particular treatment. If a majority of team or the IRB decides that the adverse event was related to intervention, [name] will stop randomizing that patient profile into that group.

Protection Against Risk: A licensed physical therapist will be present in the building during all treatment sessions. In addition, during all treadmill walking trials, a safety harness will be worn to provide assistance in the event of loss of balance. The research staff will closely monitor the subject to ensure their comfort. Any adverse events will be recorded and monitored as required by our Institutional Review Board. In the event of an adverse medical event, standard facility emergency procedures will be followed and proper personnel notified. The PI on this proposal is a licensed physical therapist with over 22 years of experience in the development and implementation of exercise interventions. On-site medical services will be available in the event of adverse events to the subjects. Subjects will be able to terminate the training or testing sessions at their request at any time without prejudice. Minimization of risk will be accomplished by monitoring vital signs every 5 minutes within prescribed criteria for termination of the training session. We will follow the American College of Sports Medicine criteria for terminating an exercise session which

includes: subject complaints of light-headedness, confusion, or dyspnea; onset of angina; excessive blood pressure changes (systolic BP greater than 220 mmHg, diastolic BP greater than 110 mmHg); and inappropriate bradycardia (drop in heart rate >10 beats per minute).

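### Sections 3.0 and 13.0 set different limits for ending a training session: systolic pressure above 200 versus 220 mmHg, and a heart-rate drop above 15 versus 10 bpm

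*Combined protocol and SAP*

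**What the plan says.** Section 3.0, under Vital Sign Monitoring, lists criteria for ending training that apply to all training groups. The blood-pressure items are "excessive blood pressure (systolic BP > 200mm Hg, diastolic BP > 110 mm Hg), or drop in systolic BP > 10 mm Hg". The text runs on into the heart-rate item: "drop in systolic BP > 10 mm Hg and inappropriate bradycardia (drop in heart rate > 15 bpm". The description of the intervention in the same section points staff to this paragraph and sets the checking schedule: "individuals will walk for 20 minutes at a 10-degree treadmill tilt, stopping each five minutes for monitoring of vital signs".

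Section 13.0, under Protection Against Risk, describes "monitoring vital signs every 5 minutes within prescribed criteria for termination of the training session" and then makes its own commitment: "We will follow the American College of Sports Medicine criteria for terminating an exercise session". For blood pressure its limits read "excessive blood pressure changes (systolic BP greater than 220 mmHg, diastolic BP greater than 110 mmHg". Its heart-rate limit, the last item in that list, reads "inappropriate bradycardia (drop in heart rate >10 beats per minute".

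Section 10.0 gives the training exposure: "Each individual will complete 12 sessions (three times a week for four weeks".

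**The concern.** Both sections govern the same event, ending a training session on vital signs taken about every five minutes, yet they print different numbers for two of the signs. A protocol may describe a safety rule in more than one place, but the limits must match, or one place must be said to take precedence. Neither is the case here.

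Different sources do not explain the difference. The Section 3.0 list cites references 48 and 49, and the reference list shows 48 to be the American College of Sports Medicine guideline. Section 13.0 names the same organisation's criteria.

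At stake is the safety of chronic-stroke participants aged 25 to 75 in training that Section 6.0 itself calls novel and intense, and whether stopping is handled alike across therapists and sessions.

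**Working it through.** The plan has no calculated figure to reproduce here. The check sets the two lists side by side and finds where they disagree.

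| Sign | Section 3.0 | Section 13.0 | Stricter |
|---|---|---|---|
| Systolic pressure | > 200 mmHg | > 220 mmHg | Section 3.0 |
| Diastolic pressure | > 110 mmHg | > 110 mmHg | same |
| Drop in heart rate | > 15 bpm | > 10 bpm | Section 13.0 |

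Both lists are worded as open, so items printed in only one of them (severe headache, the systolic drop) are not counted as conflicts.

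**Where they disagree, in whole-number readings, one sign at a time**

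- Systolic pressure: above 200 but not above 220, that is 201 to 220 mmHg. Width 220 − 200 = 20 mmHg. Only Section 3.0 stops.
- Heart-rate drop: above 10 but not above 15, that is 11 to 15 bpm. Width 15 − 10 = 5 bpm. Only Section 13.0 stops.

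**Dependence on one word.** The heart-rate band takes the *and* before bradycardia in Section 3.0 as an ordinary list conjunction. If it instead means that the systolic drop and the bradycardia must occur together, an isolated heart-rate drop never meets Section 3.0. The disputed zone is then every isolated drop above 10 bpm. The systolic band is the same on either reading.

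**What a merged rule would do.** Taking the lower limit for each disputed sign gives min(200, 220) = 200 mmHg and min(15, 10) = 10 bpm. For these two signs, stopping at systolic > 200 mmHg or a heart-rate drop > 10 bpm stops exactly when at least one current section would.

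**How often the limits are applied**

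- Checks per session: 20 min / 5 min = 4, or 3 if the check at the end of the walk is not counted.
- Per participant: 12 × 3 = 36 to 12 × 4 = 48.
- Whole trial: 60 × 36 = 2,160 (the 60 expected to remain for analysis) to 72 × 48 = 3,456 (all recruited).

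This assumes full attendance and five-minute checks in all three arms. Section 3.0 states the checks for INCLINE and DECLINE, and Section 13.0 states them generally. Checks in the overground bout are left out. These are occasions on which a limit is applied, not counts of disputed readings.

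**The case against.** The strongest reply is that both lists can be obeyed at once. Each gives conditions for stopping, and neither tells staff to continue at a systolic pressure of 210 mmHg or a heart-rate drop of 12 bpm. Staff bound by both could stop at whichever limit is met first. That is a sensible way to act, but the protocol does not state it. A therapist working from one section has no reason to look for a tighter number in the other.

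Second, Section 3.0 is the operational text, because the intervention description points to it, while Section 13.0 reads as a risk narrative. If staff follow that pointer, the 220 mmHg limit is never used and only the heart-rate difference remains. This narrows the practical risk. It does not remove it, since no rule of precedence is given and Section 13.0 makes its own commitment.

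Third, other protections remain. The diastolic limit and several symptom criteria agree. There are also rest breaks for high perceived exertion, written physician approval, a safety harness, a licensed physical therapist in the building and on-site medical services. These limit the consequences, and they are why the point is of moderate weight.

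Fourth, the number of planned checks says nothing about how often a disputed reading would occur. That is correct, and the finding does not rest on it.

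**Conclusion.** The inconsistency is real and should be corrected. Two current sections give conflicting limits for the same decision: a 20 mmHg band for systolic pressure, and a 5 bpm band for an isolated heart-rate drop. The heart-rate band is wider if the Section 3.0 wording requires both drops together. Because each section is the stricter one for one sign, following either section alone misses a limit set by the other.

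The conclusion rests on the printed numbers and on the absence of any statement of which section governs. It does not depend on which values are clinically right, which cannot be settled from the documents. The weight is moderate: it concerns safety and uniform conduct, and nothing here shows harm to the primary analysis.

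**What to change.** Keep a single list in Section 3.0 and have Section 13.0 refer to it without repeating numbers. Use the stricter value for each sign: systolic above 200 mmHg, diastolic above 110 mmHg, heart-rate drop above 10 bpm. Keep severe headache as a criterion.

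Two secondary points can be settled in the same edit, with the clinical team confirming them along with the values:

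- Reword the *and* so that it is clear whether the systolic drop above 10 mmHg and the bradycardia are separate criteria. Separate items are the cautious choice. If the present text meant them jointly, this adds a stop for an isolated systolic drop that neither section now requires.
- State the reference reading for each drop: pre-session rest or the previous five-minute check.

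The cost is a wording change and staff notification. Some sessions may end earlier. Sample size and analysis are unchanged.

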6.0 Number of Subjects

Sample Size Determination and Statistical Approach: A total of 72 individuals post-stroke will be recruited for this study. We are assuming an attrition rate of 20% resulting in a final sample size of 60 for statistical analyses, ideally 10 in each combination of baseline group (low and high Pp) and intervention (INCLINE, DECLINE, and CONTROL training). 10% is consistent with attrition rates from previous trials of locomotor rehabilitation conducted by our group,⁴³ but we have chosen a more conservative rate of 20% based on the novelty and intensity of the intervention. There will be two strata of 30 individuals each with baseline low Pp and high Pp, respectively. From those strata, using block randomization, the subjects will be equally randomized into the INCLINE, DECLINE, and CONTROL training (10 in each training cell).

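### The two lists for stopping a training session conflict on the systolic limit and the heart-rate drop, and only one of them prints a systolic-fall criterion

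*Combined protocol and SAP*

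**What the plan says.** Section 3.0, under Vital Sign Monitoring, gives the first list. It opens "For all training groups, criteria for termination of training include subject complaints of shortness of breath" and goes on through other symptoms, angina and upper blood-pressure limits (systolic 200 mm Hg, diastolic 110 mm Hg). It ends "or drop in systolic BP > 10 mm Hg and inappropriate bradycardia (drop in heart rate > 15 bpm".

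Section 13.0, under Protection Against Risk, gives a second list for the same sessions. It is introduced by "We will follow the American College of Sports Medicine criteria for terminating an exercise session which" and contains symptoms, angina, and then "excessive blood pressure changes (systolic BP greater than 220 mmHg, diastolic BP greater than 110 mmHg); and inappropriate bradycardia", with the bradycardia item set at a heart-rate drop above 10 beats per minute. The sentence before it says "Minimization of risk will be accomplished by monitoring vital signs every 5 minutes within prescribed criteria for termination of the training session".

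The INCLINE and DECLINE description in section 3.0 says "individuals will walk for 20 minutes at a 10-degree treadmill tilt, stopping each five minutes for monitoring of vital signs", followed at once by a pointer to the Vital Sign Monitoring paragraph. Section 13.0 contains no matching pointer.

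**The concern.** Both lists tell staff when to end a session, and section 13.0 rests its minimization of risk on such criteria being prescribed. A prescribed criterion should give one answer for one reading. Here two vital signs carry different printed limits, and a third sign appears in only one list.

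The stake is participant safety and consistent conduct. Staff working from section 13.0 could continue at a systolic pressure that section 3.0 says should end the session. Staff working from section 3.0 could continue through a heart-rate drop that section 13.0 says should end it. Neither list is the safer one throughout.

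The systolic-fall item adds to this. Section 3.0 notes that many participants take drugs that blunt rises in heart rate and blood pressure during exertion. It is a reasonable inference, though not a statement in the plan, that upper limits may then be less informative and a fall relatively more so.

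**Working it through.** No sample-size, power or error-rate figure is involved, so the check compares the two lists item by item.

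| Sign | Section 3.0, Vital Sign Monitoring | Section 13.0, Protection Against Risk |
|---|---|---|
| Systolic upper limit | > 200 mm Hg | > 220 mm Hg |
| Diastolic upper limit | > 110 mm Hg | > 110 mm Hg |
| Fall in systolic pressure | > 10 mm Hg | not printed |
| Fall in heart rate | > 15 bpm | > 10 bpm |
| Light-headedness, confusion, dyspnea, angina | stop | stop |
| Severe headache | stop | not printed |

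**Numeric conflicts.**
- Systolic pressure: the lists disagree for readings above 200 and up to 220 mm Hg, a band of 220 − 200 = 20 mm Hg. At 210 mm Hg, section 3.0 stops the session and section 13.0's limit is not reached.
- Heart-rate drop: the lists disagree for drops above 10 and up to 15 bpm, a band of 15 − 10 = 5 bpm. At a drop of 12 bpm, section 13.0 stops the session and section 3.0's limit is not reached.

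Both conflicts hold however the sentence in section 3.0 is parsed. The stricter limit is in section 3.0 for systolic pressure and in section 13.0 for heart rate, so adopting either list whole would loosen one criterion.

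**Systolic fall.** Take a participant whose systolic pressure falls by 15 mm Hg, with heart rate unchanged, no symptoms, and both pressures below the upper limits.
- Section 3.0, items read as separate: stop. This is the likelier reading. The comma and the word or attach the fall to the blood-pressure item, and section 13.0 sets bradycardia off as its own item after a semicolon.
- Section 3.0, items read as joint: the criterion is not met, because the heart-rate condition is missing. The wording permits this reading but it is less likely.
- Section 13.0: no printed item is met. Its blood-pressure item speaks of changes, but the brackets define it by upper limits only.

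**Reference reading.** Neither list says what a drop is measured from: the resting value, the previous five-minute check, or the session's peak. The same pair of readings could meet a criterion under one reference and not under another.

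**The case against.** The strongest reply is that the plan already names an operative list. The text describing the five-minute stops sends the reader to Vital Sign Monitoring, which covers all training groups and, on its likelier reading, makes a systolic fall sufficient alone. This stands in large part. A reader might infer that staff have no rule at all for an isolated systolic fall, and the documents do not support that. The limits are that the pointer sits in the INCLINE and DECLINE description, and that section 13.0 states that the study will follow its own list.

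A second reply is that section 13.0's list is open, since it says what the criteria include. This also stands for the missing item: the silence is an omission, and it would be wrong to read it as an instruction to continue. Whether the external exercise criteria named there contain a systolic-fall item cannot be settled from these documents. The reply does not dispose of the numeric conflicts, because a printed limit for a listed sign states when that sign counts.

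A third reply is that the unlisted case is narrow. Light-headedness, confusion, dyspnea and angina end a session under both lists, research staff watch participants closely, and a licensed physical therapist is in the building. This confines the systolic-fall gap to an asymptomatic isolated fall. It does not narrow the two numeric bands in the same way, since they turn on the printed limits.

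**Conclusion.** The concern holds as a failure to harmonise two safety lists. The firm part is the pair of numeric conflicts: systolic pressure above 200 and up to 220 mm Hg, and heart-rate drop above 10 and up to 15 bpm. The weaker part is the systolic-fall item, which is printed in one list only and loosely worded there.

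The practical size cannot be estimated, because the documents give no frequency for any of these readings. The number of scheduled vital-sign checks would not measure it either, since it says nothing about how many checks would fall in a disputed band.

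The conclusion assumes that both lists apply to the same training sessions, as their wording indicates, and that some staff may work from section 13.0 despite the pointer in section 3.0. A reader might go further and infer harm to the endpoints or bias between arms. Nothing in the documents supports that, and it is not claimed. This is a modest safety point that is worth correcting because the correction is simple.

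**What to change.** Keep one list, in section 3.0 under Vital Sign Monitoring, and replace the list in section 13.0 with a cross-reference to it. In that list:

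- Make each item sufficient alone, separated by semicolons: systolic pressure above 200 mm Hg or diastolic above 110 mm Hg; a fall in systolic pressure of more than 10 mm Hg; or inappropriate bradycardia.
- Use the stricter printed limit for each sign (systolic 200 mm Hg, heart-rate drop 10 bpm) unless the clinical team documents a reason for the other. A bare cross-reference to the present section 3.0 list would move the heart-rate limit to the looser 15 bpm by default.
- State the reading from which a drop is measured.
- Keep the symptom items already in section 3.0.

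The cost is a short rewording in two sections, with no new measurements. The downside is possibly some extra stopped sessions; the documents do not allow their number to be estimated.
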